7. DEMOGRAPHIC, OTHER BASELINE CHARACTERISTICS AND MEDICATION

7.1. PATIENT DISPOSITION AND WITHDRAWALS

For all subjects screened the following will be presented:

- Number of subjects screened
- Number (%) of subjects who failed screening
- Number (%) of subjects who met the eligibility criteria, but didn't enter the study treatment phase (with reasons)

The above information will only be presented in the 'Overall' column and percentages will use the number of subjects screened (i.e. Screened population) as the denominator.

For the Safety population the following will be presented:

- Number of subjects dosed (Enrolled)
- Number (%) of subjects who withdrew from the study (along with reasons)
- Number (%) of subjects who completed the study
- Number (%) of subjects who chose to enter the extension study (Study LTI-302)

- Number (%) of subjects in each analysis population

Percentages will use the number of subjects dosed (i.e. Safety population) as the denominator.

A Kaplan-Meier plot will present the time to study drug discontinuation. Subjects who transition to Study LTI-302 will be censored on the day of their transition.

For each scheduled visit the following will be presented using the Safety population:

- Number (%) of subjects who had the potential to reach the visit
- Number (%) of subjects who attended the visit (including only clinic visits)
- Number (%) of subjects who withdrew from the study prior to the visit
- Number (%) of subjects who missed the visit

Their potential to reach a visit is based on the duration of time they could have been in the study, from their first dosing date till their date of transitioning to Study LTI-302 or, for those subjects who withdraw from LTI-301, the date when subjects started transitioning to LTI-302 (18th July 2019).

The algorithm will be:

1. Did they have the visit within 7 days of their last dose of study treatment?
 - a. If yes, then **Yes to Potential and Attended Visit**
 - b. If no, go to 2
2. Did they have the potential to have the visit?
 - a. If yes, then go to 3
 - b. If no, then **No to Potential**
3. Did they withdraw prior to the visit?
 - a. If yes, then **Yes to Potential and Withdraw prior to the visit**
 - b. If no, then **Yes to Potential and Missing**

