6. GENERAL ASPECTS FOR STATISTICAL ANALYSIS

6.1. GENERAL METHODS

Subjects differ by treatment history prior to entry to Study LTI-301 - the two groups will be referred to as the Transition and Add-On Groups. For all summary tables data will be presented for all subjects (Overall) and by group.

Continuous variables will be summarized using the number of non-missing observations (n), mean, standard deviation (SD), standard error (SE), median, minimum and maximum. Categorical variables will be summarized using frequencies and percentages.

Categorical shift tables will include marginal totals.

Unless otherwise specified, the estimated mean and median for a set of values should be printed out to 1 more decimal place than the original values, and SD and SE should be printed out to 2 more decimal places than the original values. The minimum and maximum should report the same number of decimal places as the original values.

Percentages will be displayed with 1 decimal place; except percentages will not be presented when the count is zero and 100% will be presented as an integer. The number of subjects in the analysis population will be the denominator.

Unless stated otherwise, baseline will be taken as the last available non-missing assessment prior to study drug administration (Day 1).

In by-visit summary tables, the baseline will be summarized using all available data, but also for each visit using only the baseline data from subjects with available data at the visit; hence the mean change from baseline will equal the mean visit value – mean baseline value.

Throughout this document ‘change from baseline’ refers to the actual change from baseline (i.e. visit value – baseline value).

All data will be listed separately for each group. Data listings will present study days in addition to dates, where study day is derived as (assessment date – first day of dosing + 1).

Since there is no formal hypothesis testing, no adjustment for multiplicity will be made for inferential statistical comparisons within or between groups.

Programming of analyses, tables and listings will be performed using R Version 3.4.0 or higher (R Foundation for Statistical Computing, Vienna, Austria) or SAS® Version 9.3 or higher (Cary, North Carolina, US).

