6.2.5. SUMMARY TABLE PRESENTATIONS

In summaries for continuous data, the number of missing values will be presented. The missing count will not include subjects who have discontinued at earlier visits or not had the potential to reach the visit (i.e. subject transitioned to extension study prior to reaching the visit).

In summaries for categorical data the following categories will be included:

- No potential to reach the visit
- Withdrew prior to the visit
- Missing

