6.4. VISIT WINDOWS

Data will be assigned to visits using windowing (see table below). If more than one assessment (including the early termination or unscheduled assessments) falls within the same defined window, the assessment closest to the target day with non-missing data will be considered for analysis; however, with the exception of laboratory and vital sign data, the visit must be within 7 days of the final dose of study treatment. For laboratory and vital sign data the assessment must be no more than 1 day after the final dose of study treatment. If two qualifying assessment dates are at the same distance from the target day, the latest assessment with non-missing data will be taken for analysis.

Visit	Target Day	Analysis Window	Interval
Baseline ^a	1 ^b	Day -30 to Day 1	
Week 2	14	2 -22	21
Month 1	30	23 – 45	23
Month 2	60	46 – 90	45

Visit	Target Day	Analysis Window	Interval
Month 4	120	91 – 150	60
Month 8	240	211 – 270	60
Month 12	360	331 – 390	60
Month 16	480	451 – 510	60
Month m	30m	(30m - 29) – (30m + 30)	60

^a Baseline is the last assessment taken prior to the start of study treatment.

^b Day 1 represents the first day of study treatment.

Please note that telephone visits are not included as only log data will be collected at those visits (e.g. AEs and concomitant medications).

These visit windows will be reviewed and may be updated prior to reporting. Any assessments that fall outside of these windows will be reviewed on a case-by-case basis, and decisions on their handling will be fully documented prior to reporting. Data collected outside these windows will only be listed.

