7.5. EXTENT OF EXPOSURE

The duration of treatment will be summarized as both a continuous variable using descriptive statistics and as a categorical variable (e.g., <2 months, 2 to <4months, 4 to <8 months..). Duration of treatment is defined as (date of last dose – date of first dose +1). The duration will be summarized for each dose and overall.

For these summaries a month will be taken to be 28 days in duration.

At Months 2, 4 and 8 (Study Days 56, 112 and 224) the average daily dose (mcg) will be summarized. Summaries will be generated for all subjects who had the potential to reach the visit (taking dose as 0 for those who have withdrawn prior to the visit) and for all subjects

still ongoing in the study at the visit.

Dose shifts from baseline will also be presented by visit.

The number and percentage of Transition subjects with sustained transition treatment through the end of Month 2 will be tabulated by initial dose and overall, where sustained transition treatment is defined as:

- treatment with LIQ861 through at least 2 months beyond transition from Tyvaso
- no interruptions to study treatment totaling more than 7 days prior to the end of Month 2
- no treatment with any prostacyclin or prostacyclin analogs apart from administration of LIQ861

The number and percentage of subjects on each dose of LIQ861 will also be tabulated against the previous Tyvaso dose for Transition subjects at Months 2, 4, 8 and 12.

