9.2. NYHA FUNCTIONAL CLASS

NYHA functional class will be assessed at Screening, Baseline, Week 2 and Months 1, 2, 4 and every 4 months thereafter.

NYHA Functional Class will be summarized categorically at each Visit (Week 2 and Months, 2, 4, 8 and 12). A shift table for changes from baseline will also be presented.

The proportion of subjects who improve their functional class will be estimated for each group at each visit (Week 2 and Months 2, 4, 8 and 12) along with its 95% 2-sided binomial confidence interval. Those subjects who didn't have the potential to reach the visit will be taken as missing, but those who withdrew will be taken as not improving.

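### SAP 7.1 gives withdrawn subjects an earlier end date for potential to reach a visit than subjects who stay, so late-enrolled withdrawals can drop out of the NYHA improvement and Month 8 dose denominators

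*SAP*

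**What the plan says.** SAP 7.1 measures potential "from their first dosing date till their date of transitioning to Study LTI-302". Withdrawals get a separate, fixed end point: "for those subjects who withdraw from LTI-301, the date when subjects started transitioning to LTI-302 (18th July 2019". A three-step algorithm follows.

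- Step 1 asks: "Did they have the visit within 7 days of their last dose of study treatment"? A yes gives potential and attendance at once.
- Step 2 tests potential for everyone else. A no ends the algorithm at no potential.
- Step 3 asks about withdrawal, but only of those who passed Step 2.

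Two later outputs use this classification.

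- **SAP 9.2, NYHA improvement.** Those who did not "have the potential to reach the visit will be taken as missing, but those who withdrew will be taken as not improving".
- **SAP 7.5, average daily dose.** One summary covers subjects with potential, "taking dose as 0 for those who have withdrawn prior to the visit". A second covers only subjects still in the study.

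The general percentage rule in SAP 6.1 is "The number of subjects in the analysis population will be the denominator". For categorical summaries, SAP 6.2.5 lists no potential, withdrawn before the visit, and missing as separate categories. SAP 6.4 says "Data will be assigned to visits using windowing", with target days 240 and 360 and windows opening on Days 211 and 331. SAP 7.1 does not say which of these days potential is judged on.

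**The concern.** Sections 9.2 and 7.5 mean withdrawal to count against the drug, as no improvement or as zero dose. The classification in 7.1 can undo that. Take two subjects with the same late first-dose date. One stays and attends the visit after 18 July 2019, and is counted. The other withdraws before the visit and is sent to no potential at Step 2, so the withdrawal question is never put. Whether a subject is in the denominator then depends partly on outcome.

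At stake are the NYHA improvement proportions at Months 8 and 12, the Month 8 mean dose among subjects with potential, and the 7.1 count of withdrawals before each visit, which can only fall.

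**Working it through.** The plan gives no figure to reproduce here: first-dose, withdrawal and transition dates are not reported.

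**1. Cut-off dates.** SAP 6.1 defines study day as assessment date − first dosing day + 1. The latest first dose that reaches Day d by 18 July 2019 is therefore 18 July 2019 − (d − 1) days.

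| Output | Day d | Days subtracted | Latest first dose |
|---|---|---|---|
| NYHA Month 8, target day | 240 | 239 | 21 Nov 2018 |
| NYHA Month 8, window opening | 211 | 210 | 20 Dec 2018 |
| NYHA Month 12, target day | 360 | 359 | 24 Jul 2018 |
| NYHA Month 12, window opening | 331 | 330 | 22 Aug 2018 |
| Month 8 dose (SAP 7.5) | 224 | 223 | 7 Dec 2018 |

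A withdrawn non-attender first dosed after these dates has no potential.

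**2. Was later entry possible?** Protocol Amendment 2 is dated 7 January 2019, and Protocol 5.3 directs dosing for future PK patients. Amendment 3, dated 20 March 2019, changed the eGFR eligibility limits; a subject first dosed that day was at Day 121 on 18 July 2019. Entry was still planned after every cut-off above. This does not show that any withdrawn subject entered then.

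**3. Direction and ceiling.** Let A be attenders, W the withdrawn subjects counted as having potential, and p the improvement rate among attenders. If missing in 9.2 means excluded, and leaving aside missed assessments, the result is p × A/(A + W). An earlier end date for withdrawals lowers W and leaves A alone, so the result can only rise. With w the share withdrawn by the visit, the relative rise is at most 1/(1 − w) − 1. At an assumed 0.20 withdrawals per year:

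- Month 8: w = 1 − exp(−0.20 × 240/365.25) = 0.123; ceiling 14.0%.
- Month 12: w = 1 − exp(−0.20 × 360/365.25) = 0.179; ceiling 21.8%.

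**4. Illustration by counts.** Assume 24 improved of 80 with potential, 30.0%. Relabelling 1, 3 or 5 withdrawals gives 24/79 = 30.4%, 24/77 = 31.2% or 24/75 = 32.0%.

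**5. Simulation.** Assumptions: p = 30%; entry uniform over 4–14 or 4–18 months before 18 July 2019; transitions spread over 1 to 6 months after that date, or made at the next 4-monthly visit. The reference uses each withdrawn subject's would-be transition date. Ranges are over the scenarios, with potential judged at the target day.

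| Withdrawals per year | NYHA Month 8 | NYHA Month 12 | Month 8 mean dose |
|---|---|---|---|
| 0.20 | +0.15 to +1.3 points | +0.3 to +3.2 points | +0.5% to +4.0% |
| 0.10 | +0.1 to +0.7 points | +0.2 to +1.8 points | +0.3% to +2.0% |

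At 0.20 the reference proportions are 0.30 × (1 − 0.123) = 26.3% and 0.30 × (1 − 0.179) = 24.6%. The largest relative rises, 5.0% and 13.0%, lie under the ceilings. With planned rule and reference both judged at window opening, the NYHA ranges at 0.20 are about +0.15 to +1.0 and +0.3 to +2.6 points.

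**The case against.** **A fixed date is defensible.** Withdrawn subjects have no transition date, and the first transition date avoids counting as failures people who might have transitioned before the visit. That stands as a reason for the choice. It does not remove the asymmetry with subjects who stayed.

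**The order of tests is not really open.** A reader might infer that 9.2 leaves a withdrawn subject without potential unclassified, since both of its clauses could apply. The three categories in SAP 6.2.5 match the exclusive outcomes of 7.1, so potential is tested first. The tables would also show the no-potential count, though not how many of those subjects had withdrawn. (The 6.2.5 sentence "The missing count will not include subjects who have discontinued at earlier visits" concerns continuous data only.)

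**The 6.1 denominator could cancel the NYHA effect.** If the whole analysis population is the denominator, the proportion does not move. But then the distinction in 9.2 between missing and not improving would do nothing, so exclusion is the natural reading. It should be stated.

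**The effect is small against sampling error.** For 24/80 the 95% half-width is 1.96 × √(0.3 × 0.7/80), about 10 points. This stands.

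**Could the effect go either way?** Comparing the rule at window opening with a target-day reference gives values down to −0.2 points (Month 8) and −0.7 (Month 12) at 0.20 per year. Those negatives come from mixing two judging days. They show that the unstated day matters, not that the end date can lower the result.

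**Conclusion.** The point holds as a minor one. Followed as written, SAP 7.1 makes potential depend on outcome, and late-enrolled withdrawals leave denominators in which 9.2 and 7.5 mean them to count. Against the same rule with a later end date for withdrawals, the NYHA proportion can only rise. The mean dose rises for subjects already off drug at Day 224; a subject still dosing then who withdraws later is an exception.

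This rests on three readings: missing in 9.2 means excluded, 7.5 uses the 7.1 classification, and potential is judged on one consistent day. The simulated sizes also rest on the assumed entry, transition and withdrawal patterns.

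A reader might infer that the reported results are inflated. The documents do not support that: the size is unknown, and it is zero if no withdrawn non-attender was first dosed after the cut-offs or, on the target-day reading, if all transitions fell on 18 July 2019. Nor does the point reach the study's main conclusions. The primary TEAE endpoint, the Kaplan-Meier plot, the MMRMs and the 7.5 summary of ongoing subjects do not use the rule, and the affected outputs are exploratory or descriptive.

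**What to change.** Keep the planned analysis. Add one sensitivity analysis of NYHA improvement at Months 8 and 12 and of the Month 8 average daily dose. In it, potential for withdrawn subjects ends at the last observed LTI-302 transition date instead of 18 July 2019. Withdrawn subjects who then have potential count as not improving or, if off drug at Day 224, as dose 0. Show it beside the planned result. The two bracket the effect of the end date, no attended visit is lost, and subjects who entered after Amendment 2 are kept.

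In the same edit, state in 7.1 whether potential is judged at the target day or at window opening, and in 9.2 that the denominator is subjects with potential.

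The cost is a few sentences and one flag from dates already in the data. SAP section 2 allows amendments before database lock. The downside is that the added analysis is a conservative bound: it can count as failures some subjects who would have transitioned before the visit.

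One common cut-off of 18 July 2019 for everyone is a tempting alternative. All three target-day cut-offs precede Amendment 2, which revised the Tyvaso transition starting doses. That analysis would drop every later entrant, so a difference from the planned result, above all in dose, could not be attributed to the potential rule alone. If it is shown as well, say so.

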7.2. DEMOGRAPHIC CHARACTERISTICS

These data were reported in the Month 2 clinical study report. The outputs will be repeated for this final study report.

7.3. MEDICAL HISTORY AND CONCOMITANT DISEASES

These data were reported in the Month 2 clinical study report. The outputs will be repeated for this final study report.

7.4. PRIOR AND CONCOMITANT MEDICATIONS

Prior medications will be defined as those medications started prior to the administration of study drug on Day 1. Concomitant medications will be defined as those medications taken following administration of study drug on Day 1. Hence medications started before receiving the study dose, but continuing after will be considered as both prior and concomitant medications. The listing of medications will identify prior and concomitant medications.

Prior medications (PAH and non-PAH) were reported in the Month 2 clinical study report. The outputs will be repeated for this final study report.

Concomitant medications will be presented for the Safety population by therapeutic class and preferred term (PT), using the WHO-Drug Dictionary (WHO-Drug; March, 2017), with frequencies and percentages. A subject who took the same medication more than once will be counted only once. Separate summaries will be presented for PAH disease specific medications and non-PAH disease specific medications.

In the summary tables, classes/PTs will be presented by decreasing frequency of subjects overall. In cases of classes/PTs with equal frequencies, medications will be sorted alphabetically.

The PAH disease specific medications ongoing on Day 1 will be summarized. The summary will include the number and percentage of subjects on 0, 1 or 2 medications, and also the number and percentage of subjects on each combination. Shift from baseline tables will also be presented (for number [0, 1 or 2] and combinations) at Months 4, 8 and 12.

The shift table will also be presented to the subject's end of the study, but will be split by those who completed LTI-301 and those who withdrew from LTI-301. Please note, for those who withdrew from LTI-301 the intention is to only consider medications taken before study drug discontinuation and not additional medications taken afterwards.

7.5. EXTENT OF EXPOSURE

The duration of treatment will be summarized as both a continuous variable using descriptive statistics and as a categorical variable (e.g., <2 months, 2 to <4months, 4 to <8 months..). Duration of treatment is defined as (date of last dose – date of first dose +1). The duration will be summarized for each dose and overall.

For these summaries a month will be taken to be 28 days in duration.

At Months 2, 4 and 8 (Study Days 56, 112 and 224) the average daily dose (mcg) will be summarized. Summaries will be generated for all subjects who had the potential to reach the visit (taking dose as 0 for those who have withdrawn prior to the visit) and for all subjects

still ongoing in the study at the visit.

Dose shifts from baseline will also be presented by visit.

The number and percentage of Transition subjects with sustained transition treatment through the end of Month 2 will be tabulated by initial dose and overall, where sustained transition treatment is defined as:

- treatment with LIQ861 through at least 2 months beyond transition from Tyvaso
- no interruptions to study treatment totaling more than 7 days prior to the end of Month 2
- no treatment with any prostacyclin or prostacyclin analogs apart from administration of LIQ861

The number and percentage of subjects on each dose of LIQ861 will also be tabulated against the previous Tyvaso dose for Transition subjects at Months 2, 4, 8 and 12.

7.6. STUDY TREATMENT COMPLIANCE

Compliance will be assessed using subject data recorded in the drug accountability form of the eCRF. The compliance rate for each subject will be computed as $100\% \times (\text{actual number of capsules taken over the study period}) / (\text{designated total number of capsules that should have been taken over the study period})$. Study period is defined as the number of days from Day 1 till their last day of dosing. The number of dosing days will take account of dose interruptions due to AEs. If a subject fails to return study medication compliance will be provided as a range, assuming that either all or none of the unreturned medication was returned.

8. SAFETY ENDPOINTS

All safety evaluation will be performed using the Safety population. The mITT population will only be used where specifically mentioned.

8.1. ADVERSE EVENTS

AEs will be coded using MedDRA version 20.1.

AEs will be considered TEAE unless there is clear indication that the event occurred prior to the first dose of study drug. AEs present prior to study drug administration that increased in severity or relationship to study drug afterwards will also be classed as TEAEs.

All AEs that occur after the first dose of study drug will be considered to be 'treatment-

'emergent' with the exception of AEs that occur more than 7 days after the last dose of study drug.

Events with missing or partial dates will be handled such that in the absence of contradictory information an AE is treatment emergent (see Section 6.2).

Only TEAEs will be included in the summary tables.

An overall summary will present the number of subjects with:

- any TEAE*
- any TEAE considered as related to study drug (evaluated by the investigator as Related or severity not reported)*
- any serious TEAE*
- any serious TEAE considered as related to study drug*
- Maximum severity TEAEs of mild, moderate or severe; i.e. a subject with TEAEs at different intensities will be summarized at the most severe intensity
- Maximum severity TEAEs considered as related to study drug of mild, moderate or severe; i.e. a subject with TEAEs at different intensities will be summarized at the most severe intensity
- any TEAE leading to study drug discontinuation (i.e. TEAEs reported as having either an action taken as 'Drug Withdrawn') and/or Study Discontinuation*
- any TEAE considered as related study drug discontinuation (i.e. TEAEs reported as having either an action taken as 'Drug Withdrawn') and/or Study Discontinuation *
- any TEAE leading to death*

The table will also include the total number of TEAEs reported for those flagged (*). The total number of unique terms within subjects will also be presented for those flagged (*), counting each TEAE PT only once within each subject.

This overall summary will be presented for both the Safety and mITT populations.

This summary will also be produced using the Safety population for the following:

- the subgroups in Section 6.3
- those TEAEs with an onset up to the Month 2 visit (inclusive) and those with an onset after the Month 2 visit separately.

The number and percentage of subjects with TEAEs will be presented by system organ class (SOC) and PT for both the Safety and mITT populations. Subjects with multiple TEAEs within a SOC or SOC/PT combination will be counted only once for that SOC or SOC/PT combination.

A similar summary will be presented for the Safety population of TEAEs considered as study drug related.

The 'all causality' summary will also be produced using the Safety population for the following:

- the subgroups in Section 6.3
- those TEAEs with an onset up to the Month 2 visit (inclusive) and those with an onset after the Month 2 visit separately.

SOC and PT summaries of TEAEs by maximum severity (mild, moderate or severe) will be presented for all TEAEs and also for those considered as related to study drug.

All summaries will be ordered by descending frequency of total number of subjects within each SOC and then similarly by decreasing frequency of total number of subjects within each PT, in the overall column. In cases of SOCs or PTs with equal frequencies, AEs will be sorted alphabetically.

All TEAEs will be listed by subject and AE onset day. AE duration (stop date/time – start date/time) will be included in the listing; where applicable imputed data will be used for the calculation of AE duration, but the original date information will be presented in the listing.

The following separate listings will also be provided:

- serious AEs
- TEAEs leading to study drug discontinuation (i.e. TEAEs reported as having either an action taken as 'Drug Withdrawn') and/or Study Discontinuation

If there are any deaths a listing will include the date of death and the adverse event(s) associated with death.

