6.2.7. Follow-up for Withdrawn Patients

Follow-up should occur for all patients that are removed from the study (Early Termination) for at least 4 months after receiving the last dose of LIQ861 or until all TEAEs are resolved or stabilized. If the patient was withdrawn from treatment with the study drug for clinical worsening, follow-up visits should be scheduled at the discretion of the investigator for the longer of the following periods:

- at least 4 months from receiving the last dose of LIQ861,
- until, in the opinion of the investigator, the patient is no longer clinically worsened from his or her baseline state, or
- until, in the opinion of the investigator, clinical worsening from baseline state is no longer attributed to treatment with LIQ861.

Follow-up visits may be conducted as telephone calls or in person visits at the Investigational site. At a minimum, follow-up visits should occur at approximately 2 weeks \pm 2 days, and at 2 months and 4 months after receiving the last dose of LIQ861 and include the following assessments:

- Treatment-Emergent Adverse Events
- Concomitant medications

If the patient was withdrawn from treatment with the study drug for clinical worsening, additional assessments for the signs and symptoms that lead to judgement of clinical worsening should be made at all follow-up visits within 4 months of Early Termination or until the signs and symptoms that lead to judgement of clinical worsening are resolved.

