7. ADVERSE EVENTS

The Investigator is responsible for the detection and documentation of events meeting the definition of an AE or SAE as provided in this protocol. Only Treatment-Emergent AEs (TEAEs) and SAEs (occurring after the first inhalation of LIQ861, or Tyvaso in the PK sub-study, through the appropriate follow-up period) will be recorded in this study.

Definitions and terminology relevant to IND Safety Reports, as referenced in the U.S. Code of Federal Regulations, are addressed below.

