7.1. Definition of a Treatment-Emergent Adverse Event

An AE is any untoward medical occurrence associated with the use of a drug in humans, whether or not considered drug related. All AEs that occur after the time of treatment with the investigational product will be considered a Treatment Emergent AE (TEAE).

A TEAE can be any unfavorable and unintended sign (e.g., an abnormal laboratory finding), symptom, or disease temporally associated with the use of a drug, without any judgment about causality.

A TEAE **does** include any:

- Exacerbation of a pre-existing illness.
- Increase in frequency or intensity of a pre-existing episodic event or condition.
- Condition detected or diagnosed after study drug administration even though it may have been present prior to the start of the study.

- Continuous persistent disease or symptoms present at baseline that worsen following the start of the study.
- Events considered by the investigator to be related to study-mandated procedures.
- Abnormal assessments (e.g., change in physical examination), if they represent a clinically relevant finding, that were not present at Baseline or worsened during the course of the study.
- Laboratory test abnormalities, if they represent a clinically relevant finding, symptomatic or not, which were not present at Baseline or worsened during the course of the study.

A TEAE **does not** include a/an:

- Medical or surgical procedure (e.g., surgery, endoscopy, tooth extraction, transfusion); the condition that leads to the procedure is an AE.
- Situations where an untoward medical occurrence has not occurred (e.g., hospitalization for cosmetic elective surgery, social and/or convenience admissions).
- Overdose of either study drug or concurrent medication without any signs or symptoms.
- Hospitalization for elective treatment of a pre-existing condition that did not worsen during the study is not considered an AE.

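### SAP 8.1 stops counting adverse events 7 days after the last dose, so later-starting events that the protocol collects as TEAEs enter no incidence table

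*SAP*

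**What the plan says.** The primary endpoint, in Protocol 3.2.1 and SAP 4.1, is the incidence of TEAEs and SAEs.

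On what counts as a TEAE, Protocol 7.1 says: "All AEs that occur after the time of treatment with the investigational product will be considered a Treatment Emergent AE (TEAE". It gives no last day. Protocol 7 has TEAEs and SAEs recorded from the first inhalation "through the appropriate follow-up period". Protocol 6.2.7 follows every patient removed from the study "for at least 4 months after receiving the last dose of LIQ861 or until all TEAEs are resolved or stabilized". It sets minimum contacts at about 2 weeks, 2 months and 4 months after the last dose, and each contact asks about TEAEs. For withdrawal because of clinical worsening, the longest of several periods applies.

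SAP 8.1 opens with a rule that likewise has no upper limit: "AEs will be considered TEAE unless there is clear indication that the event occurred prior to the first dose of study drug". The next paragraph adds one, "with the exception of AEs that occur more than 7 days after the last dose of study drug". The section then states: "Only TEAEs will be included in the summary tables". For incomplete dates the default is inclusion: "in the absence of contradictory information an AE is treatment emergent".

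SAP 8.1 also plans listings of serious AEs and of deaths that are not worded as TEAE-only, and SAP 6.1 says that all data will be listed.

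**The concern.** The same term has two meanings. The protocol collects an event starting, say, three weeks after the last dose as a TEAE, and the SAP then removes it from the tables under that name. The SAP neither explains the 7-day limit nor marks it as a departure from the protocol. Its own opening rule in 8.1 would include the event.

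The limit acts directly on the primary endpoint. That endpoint names SAEs beside TEAEs, but the overall summary in SAP 8.1 has rows only for serious TEAEs and for TEAEs leading to death. A new SAE or fatal event starting after day 7 thus has no row in which it can be counted. The patients under follow-up at that time are those who left early, including those withdrawn for a TEAE or for clinical worsening. It is reasonable to suppose that their short-term risk is higher, but the documents give no figure for it. In a study whose primary objective is long-term safety and tolerability, a reader of the final report would see incidence rates that do not match the protocol's definition and would not be told so.

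**Working it through.** The plan gives no figure on this point, so the check is a comparison of texts with some simple arithmetic.

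**Step 1: what happens to each kind of event.** The table takes early-termination patients, reads the SAP's word *occur* as onset, and counts days from the last dose.

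| Event | Protocol 7, 7.1, 6.2.7 | SAP incidence tables | SAP listings |
|---|---|---|---|
| Starts on treatment or by day 7 | TEAE | Counted | Listed |
| Starts by day 7, patient dies later from it | TEAE | Counted, including in the row for TEAEs leading to death | Listed |
| Starts by day 7, first reported at the 2-week contact | TEAE | Counted | Listed |
| Newly starts after day 7, full date | TEAE | **Not counted** | Serious or fatal: specific listings. Other: only through the general rule in SAP 6.1 |
| Newly starts after day 7, start date missing or partial | TEAE | May be counted, because SAP 8.1 defaults to inclusion and SAP 6.2.3 imputes early dates | Listed |

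The two documents part company on the fourth row, and can do so on the fifth.

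**Step 2: length of the window against the follow-up.** Inputs are the 7 days in SAP 8.1, the 4 months in Protocol 6.2.7, and the SAP's two month lengths (30 days in the visit windows of SAP 6.4, 28 days in SAP 7.5).

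- 30-day months: 4 × 30 = 120 days. Inside the window 7/120 = 5.8%; outside 113/120 = 94.2%.
- 28-day months: 4 × 28 = 112 days. Inside 7/112 = 6.25%; outside 105/112 = 93.75%.

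The first required contact falls on days 14 ± 2, that is, days 12 to 16. Each contact therefore comes after the window has closed, although it can still pick up events that began inside it.

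**Step 3: what one missed patient is worth.** SAP 6.1 uses the number of subjects in the analysis population as the denominator, and SAP 5.2 gives 121 in the Safety Population (55 Transition, 66 Add-On). A patient whose only qualifying event starts after day 7 would change a row by:

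- Overall: 1/121 = 0.8 percentage points
- Transition: 1/55 = 1.8 percentage points
- Add-On: 1/66 = 1.5 percentage points

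A patient already counted in that row adds nothing. The documents do not say how many patients would be added, so no total can be computed.

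**The case against.** The strongest reply is that a short window after the last dose is a sound on-treatment definition. The drug is inhaled four times a day and its PK profile is sampled over 4 hours. Protocol 7.1 itself speaks of a temporal link with drug use, and Protocol 8 leaves analysis detail to the SAP. The SAP also uses a 7-day limit for most visit data (SAP 6.4) and for attendance (SAP 7.1), so the rule is not arbitrary within the plan. Patients who worsen may be withdrawn and given rescue therapy, so late events in this uncontrolled study may reflect disease or other treatment. Pooling them would mix time on and off drug, and only for the patients who left early. This stands. It is a reason to keep the 7-day tables and to show later events separately. It does not explain why the protocol's term is narrowed without comment, or why late SAEs have no incidence at all.

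It also stands that nothing need be hidden. Serious AEs and deaths have listings not confined to TEAEs, and with 121 subjects these can be read one by one. A listing, however, is not the incidence that the endpoint calls for.

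Three stronger readings are tempting, and the documents do not support them.

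- A reader might infer that about 94% of post-withdrawal events are lost. The figure is a share of calendar days, for early-termination patients only, and leaves out all on-treatment time. The 4-month period also has the alternative of ending when TEAEs resolve or stabilize, although the minimum contacts run to month 4.
- A reader might infer that everything reported at the three contacts is dropped because all three come after day 7. The rule works on when the event occurs, not on when it is reported.
- A reader might infer that a death following withdrawal for worsening is left out. If the fatal event began by day 7, the death still counts.

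**Conclusion.** The point holds for a defined class: fully dated AEs, SAEs and fatal events that newly start more than 7 days after the last dose. The protocol counts and collects them as TEAEs, whereas the SAP leaves them out of every incidence table for the primary endpoint. The departure is unstated and unexplained, and SAP 8.1 is not consistent within itself.

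The size is unknown because the documents give no count of such events. Each additional patient would move an overall row by 0.8 percentage points. Nothing in the documents shows that a safety conclusion would change, and no formal hypothesis test depends on it (Protocol 8.4).

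The verdict assumes that *occur* in SAP 8.1 means onset, and that the contacts in Protocol 6.2.7 were made and their findings recorded. If *occur* were read more broadly, the excluded class would be less clear, which is a further reason to define it.

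**What to change.** In SAP 8.1:

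1. Keep the existing tables and label them as the on-treatment analysis, covering events with onset from the first dose to 7 days after the last dose. Reword the opening TEAE sentence to agree.
2. State that this limit departs from Protocol 7.1, and give the reason.
3. Add an overall summary of AEs, SAEs and deaths from the first dose to the end of protocol follow-up, with a breakdown by system organ class and preferred term for SAEs and deaths. Show events starting after day 7 in a separate column or block, with a note that they may reflect disease or rescue therapy.

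The cost is one or two extra tables from data that the protocol already collects. Reported incidence may rise; by how much cannot be said from the documents. No visit, assessment or treatment rule changes.
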